### 4.3.3 Other features to minimise bias

Loss to follow-up will be minimised by the regular study visits; research nurses will immediately contact a participant in the event of a missed visit to ascertain the reason and, wherever possible, to arrange an alternative appointment. Loss to follow-up in the IVAN trial which

included an elderly visually impaired trial population and monthly hospital visits and was managed by CTEU Bristol, was 4% per annum among surviving participants [11]. Selective reporting will be avoided by providing detailed definitions of all outcome measures in the protocol and by writing a statistical analysis plan before any comparative analysis is performed. Any deviations from the statistical analysis plan will be reported and justified.

#### 4.4 Trial population

##### 4.4.1 Inclusion criteria

Participant may enter study if ALL of the following apply

1. Participants will be aged  $\geq 18$  years and  $\leq 60$  years
2. Visual impairment due to CSCR of  $\geq 4$  months duration defined as:
  - a. subfoveal presence of SRF on OCT  
AND
  - b. characteristic appearance of CSCR on FFA and Indocyanine-green angiography (ICGA).  
AND
  - c. investigator believes that there is sufficient evidence from patient history, case note documentation or appearance of the macula that CSCR has been present for at least 4 months.
3. Women must have a negative pregnancy test and be willing to use effective contraception\* for the duration of the participation in the trial and for 3 months after, be surgically sterile or post-menopausal for  $>12$  months.
4. Able to provide written informed consent.

The following apply to the study eye:

5. A study eye should have an Early Treatment Diabetic Retinopathy Study (ETDRS) BCVA score greater than 53 letters and less than 86 letters.
6. A study eye should have clear ocular media and adequate pupillary dilatation to permit photography.

\* this includes: progestogen-only oral hormonal contraception, where inhibition of ovulation is not the primary mode of action, male or female condom with or without spermicide cap, diaphragm or sponge with spermicide, combined (estrogen and progestogen containing) hormonal contraception associated with inhibition of ovulation (oral, intravaginal or transdermal), progestogen-only hormonal contraception associated with inhibition of ovulation: (oral, injectable, implantable), intrauterine device, intrauterine hormone-releasing system, bilateral tubal occlusion, vasectomised partner, sexual abstinence.

NB pregnancy test only need to be repeated if there is reason to suspect the participant has become pregnant.

There are no special precautions/contraceptive requirements for male participants with female partners of child bearing potential.

It is rare but not impossible for patients to present with CSCR in both eyes or CSCR may develop in the fellow eye during the trial. We propose to measure eye-specific outcomes such as BCVA in both eyes throughout the trial, designating eyes as study eyes or not. Statistical analyses will take into account the availability of data for two eligible eyes in one patient.

If both eyes present with CSCR at baseline, the clinical trial site will decide which is the primary eye and this eye will have retinal imaging performed first. The primary eye would usually be the one with most active disease/most sub-retinal fluid. It will be identified by OCT imaging and subsequent investigations such as fluorescein and indocyanine green angiography will then be performed initially on this eye. If a patient presents with one affected eye and the fellow eye subsequently develops CSCR the eye first affected will always be the primary study eye.

#### 4.4.2 Exclusion criteria

Participant may not enter study if ANY of the following apply

1. Hyperkalaemia (serum potassium level > 5.0 mmol/L).
2. Hepatic or renal impairment (Patients with severe renal insufficiency (Estimated glomerular filtration rate, eGFR < 30 mL per minute per 1.73 m^2) or Patients with severe hepatic insufficiency (Child-Pugh Class C).
3. Pregnancy or breast feeding.
4. Known allergy to fluorescein or indocyanine green.
5. Patients receiving potassium-sparing diuretics, potassium-supplements, or inhibitors of CYP 3A4 (e.g. amiodarone, diltiazem, fluconazole, itraconazole, ketoconazole, ritonavir, nelfinavir, saquinavir, clarithromycin, telithromycin, erythromycin, verapamil, spironolactone and nefazodone)). Patients taking furosemide are eligible.
6. Patients receiving nonsteroidal anti-inflammatory drugs (NSAIDs) (e.g. ibuprofen, naproxen).
7. Patients receiving the combination of an angiotensin converting enzyme (ACE) inhibitor and an angiotensin receptor blocker (ARB).
8. Patients receiving lithium, cyclosporine or tacrolimus.
9. Hypersensitivity or known allergy to eplerenone or to any of the excipients.
10. Known hereditary problems of galactose intolerance, the Lapp lactase deficiency or glucose-galactose malabsorption.
11. Patients receiving high doses of aspirin (>75mg).

The following additional exclusions apply to a study eye only (i.e. they may be present for a non-study eye):

12. Evidence of choroidal neovascularization.
13. Previous or current treatment with eplerenone for any reason or previous or current treatment with photodynamic laser therapy / any anti-VEGF therapy in the study eye / any intra-ocular steroid use / thermal laser therapy for CSCR.
14. Presence of any other disease which could cause retinal fluid or SRF to accumulate (e.g. diabetic retinopathy\*, polypoidal choroidal vasculopathy, domed shaped maculopathy or choroidal haemangioma) or affect visual acuity.
15. Myopia > -6 dioptries

\*Diabetes alone is not an exclusion criterion.

#### 4.5 Trial interventions

Intervention: The intervention will be Eplerenone 25 mg/day increased to 50 mg/day after 1 week (as per manufacturer's recommendations for dose initiation) in addition to usual care. Treatment will be continued until there is evidence of complete resolution of SRF. The 25mg and 50mg doses will be achieved using 25mg and 50mg strength tablets respectively.

Control: placebo tablet, manufactured to match the Eplerenone tablets, with usual care.

If there is recurrence of SRF with an increase in central subfield retinal thickness (CSRT) of at least 50µm, the allocated treatment will be restarted.

Masking will be achieved by over encapsulating the tablets so that intervention and control appear identical.

Dose escalation: The patient's potassium level will be assessed at 1 week. Patients will be given the 50 mg tablets to take home but to await a phone call that to tell them whether to proceed or not (once the potassium results have been received). The potassium levels are then checked at 4 weeks. If at any time the potassium levels are out of range, study medication will be discontinued. As traumatic blood taking can raise potassium levels, in the case of a high reading the test may be repeated prior to deciding whether to discontinue treatment. If a patient restarts eplerenone during the study the same dose escalation procedure will occur i.e. patients will restart on Eplerenone 25 mg/ day increased to 50 mg/day after 1 week. Serum potassium will again be measured before initiating eplerenone therapy, within the first week and at one month after the start of treatment.

Monitoring Compliance: Patient compliance with study drug will be assessed at each visit. Compliance will be monitored by capsule counts performed by site pharmacy personnel at each visit. Compliance will be evaluated as the percentage of prescribed pills taken since the previous evaluation. If this percentage is  $\leq 70\%$  for the time period, then the patient will be categorised as non-compliant for the time period since previous evaluation. Non-compliance will not be a reason for withdrawal from the study but the reasons for non-compliance will be explored and documented. Site personnel will take extra efforts to ensure that non-compliant patients improve their compliance by frequent telephone reminders and counselling. Any deviations from the prescribed dosage regimen will be recorded.

Rules for treatment decisions: For individual patients, treatment will be stopped at week 4, month 3, 6, 9 or 12 if there is complete resolution of SRF under the fovea in the study eye. Treatment will be restarted at a subsequent visit if there is recurrence of sub-foveal SRF. Also treatment will be stopped for individual patients if they develop a complication of taking eplerenone. The most likely complications to result in treatment cessation include serum potassium levels being  $>5$  mmol/l, eosinophilia or symptomatic hypotension. Other adverse events that may result in treatment cessation are listed in section 8.1. If any serious adverse reaction to the drug / placebo occurs, the patient will be advised to stop treatment but will continue to be followed in the study unless the patient asks to withdraw from the trial. If the BCVA drops by 15 or more letters from baseline assessment, the ophthalmologist may consider alternative therapies or may decide to stop the study intervention. The use of PDT or thermal laser is not recommended unless the visual acuity drops by at least 15 letters or more from baseline assessment; even then, such treatments are not mandated but can be used at the discretion of the treating ophthalmologist. A decrease of 15 or more letters is an established criterion for a sight threatening adverse event and has been used in many clinical trials of retinal diseases. [12, 13] Treatment will also be stopped if a participant falls pregnant.

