### 4.6.2 Secondary outcomes

Secondary outcome measures are:

1. Low luminance BCVA. This is measured immediately after measuring BCVA by adding a 2 log neutral density filter and recording the number of letters read.
2. CSRT as measured by OCT recorded at 12 months, including CSRT measured at interim visits and adjusted for baseline CSRT.
3. Change in sub-retinal fluid thickness as measured by OCT
4. Systemic and ocular adverse events at any time during the 12 month follow-up period
5. Proportion of patients with macular atrophy of the RPE defined as hypoautofluorescence at 12 months
6. Area change in macular RPE hypoautofluorescence at 12 months.
7. Choroidal thickness as measured by enhanced depth imaging OCT at 12 months, adjusted for baseline choroidal thickness. Measurements to be made sub-foveally.
8. Proportion of patients with reduced choroidal permeability on ICG at 12 months
9. Time to resolution of SRF.
10. Classification of all study eyes as complete, partial or no resolution of SRF at each time point of the study. Partial resolution of SRF is defined as a decrease of >25 % of CMT from baseline due to resolution of SRF. A non-responder is defined as having an increase in SRF or decrease in SRF  $\leq 25\%$  from baseline. Recurrence will be defined as the appearance of new SRF in a study eye after complete resolution of SRF at any point.
11. Patient-reported visual function using Visual Function Questionnaire VFQ 25 will be assessed at baseline and 12 months.
12. Classification of all study eyes by each FFA phenotype, such as smoke stack, ink-blot and chronic epitheliopathy
13. Classification of all study eyes as early, late, or non responder. An early responder is defined as complete or partial resolution of sub-foveal SRF by 3 months. A late responder is defined as complete or partial resolution of sub-foveal SRF after 6 months.
14. Incidence of CSCR in the fellow eye as measured by OCT, FFA, ICGA or AF.

A validated ophthalmic reading centre will assess images obtained from OCT, ICGA and FFA at baseline and 12 months.

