### **5.4 Duration of treatment period**

See section 4.5

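### Section 4.5 gives two incompatible triggers for restarting study drug: one needs a CSRT rise of at least 50 µm, the other needs none

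*Protocol*

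**What the plan says.** All the operative text is in Protocol section 4.5, in two places.

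- **Restart, opening part.** "If there is recurrence of SRF with an increase in central subfield retinal thickness (CSRT) of at least" 50 µm, the allocated treatment is restarted. The fluid has no stated location, and the rise has no stated reference visit.
- **Restart, paragraph on rules for treatment decisions.** "Treatment will be restarted at a subsequent visit if there is recurrence of sub-foveal SRF". There is a location but no thickness condition.
- **Stop, opening part.** "Treatment will be continued until there is evidence of complete resolution of SRF". No location is given.
- **Stop, rules paragraph.** Drug is stopped at week 4 or month 3, 6, 9 or 12 "if there is complete resolution of SRF under the fovea in the study eye".

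Section 5.4, on duration of treatment, says only "See section 4.5". Section 5.10 covers stopping for adverse events, pregnancy and loss of 15 or more letters. It does not mention restarting.

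**The concern.** A restart rule is a dosing instruction that sites carry out at a visit, so it has to be settled in the protocol and cannot wait for the analysis plan. Here both sentences are current text and both are worded as mandatory, yet they select different patients. Two sites could treat the same eye differently and each could cite section 4.5.

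Central grading does not close the gap. Under Table 1, footnote 1, the reading centre grades OCT only at baseline and 12 months; images from other visits are graded within the study team. Section 4.5 also says "Any deviations from the prescribed dosage regimen will be recorded", and with two triggers it is unclear which one a restart decision would be compared with.

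At stake are the consistency of the regimen under test and, in the eplerenone arm, who goes back on a drug that needs potassium monitoring.

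**Working it through.** The plan has no figure to reproduce on this point, so the check sets the sentences side by side.

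**Restart.** Take an eye in which drug was stopped after resolution and fluid is seen again at a later visit.

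1. Sub-foveal fluid, CSRT rise of 50 µm or more: both sentences restart.
2. Sub-foveal fluid, CSRT rise below 50 µm: the rules paragraph restarts; the opening part is not triggered.
3. Fluid only away from the fovea, CSRT rise of 50 µm or more: the opening part restarts; the rules paragraph is not triggered. This should be less usual, because CSRT is a central measure.
4. Fluid only away from the fovea, CSRT rise below 50 µm: neither restarts.

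The sentences disagree in cases 2 and 3. If either trigger is enough, the 50 µm condition matters only in case 3 and has almost no function. If both must be met, the rules paragraph is wrong as written, because it restarts case 2 without qualification. Under either reading one sentence has to give way, and the protocol does not say which.

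**Reference visit.** Thickness at the visit where drug was stopped would normally be lower than at baseline, because the fluid has gone. The same eye can therefore pass the threshold measured from the stopping visit and fail it measured from baseline.

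**Stop.** The sentences differ for an eye with a dry fovea and residual fluid elsewhere: the opening part continues drug, the rules paragraph stops it. The protocol does use the two terms separately. Section 4.6.2 item 10 refers to SRF without location ("Recurrence will be defined as the appearance of new SRF in a study eye after complete resolution of SRF at any point"), while item 13 refers to the sub-foveal kind ("An early responder is defined as complete or partial resolution of sub-foveal SRF by 3 months"). These are outcome definitions and not dosing rules, so they show only that the unqualified word need not mean sub-foveal.

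**Length of one divergent decision.** Inputs are the visit schedule in Table 1 and the stopping visits in section 4.5.

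- Restart: the earliest stop is week 4, so recurrence can first be acted on at month 3, then at months 6 and 9. One interval is 6 − 3 = 9 − 6 = 12 − 9 = 3 months.
- Stop: week 4 is 28/30.44 = 0.92 months, so the first interval is 3 − 0.92 = 2.08 months. Later intervals are 3 months.
- A restart also repeats the week at 25 mg and calls for potassium before restarting, within the first week and at one month. Table 1 already takes urea and electrolytes at every visit, so the first of these can fall on the decision visit.

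**The case against.** The best defence is that the two restart sentences are meant to be read together: the rules paragraph gives location and timing, the opening part gives the size of recurrence that counts. That may be the intention. It does not resolve the text, because the rules paragraph is complete and unqualified as it stands, and the 50 µm condition appears only in the opening part. The paragraph's heading suggests that it governs, but on that reading the threshold drops out. The two defences lead to different triggers.

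On stopping, the defence largely succeeds. The opening part describes the intervention in general terms, and the rules paragraph gives visits, eye and location. Entry also requires subfoveal fluid (section 4.4.1), so the unqualified term can be read that way. Against this, the pilot in section 2.3, described as using similar methods, counted resolution only when fluid was absent from all OCT sections. That was a pilot outcome, however. A reader might infer two equally conflicting stop rules; the text supports only a wording mismatch.

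Site divergence is inferred and not observed. Training (section 7.2.1) and a study manual (section 10.3) may steer all sites to one reading, and the trial schema is not shown. None of these could remove a conflict in the protocol text itself. The sentence on recording deviations sits in the compliance paragraph, which is mainly about capsule counts, so it adds little weight.

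**Conclusion.** The restart rule is contradictory as written and should be corrected; the stop wording is a secondary mismatch. For restarting, the size per divergent decision is at least one 3-month interval on or off drug, plus a repeat of dose escalation and its monitoring. The documents do not show how many eyes would fall in cases 2 or 3, so no patient count is given.

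Four stronger conclusions might be inferred and are not supported:

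- **Bias in the primary comparison.** Sites are masked, the ambiguity applies to both arms, and section 6.1 analyses by allocation. The sample size inputs in section 4.7 do not depend on the restart rule.
- **Many months of wrong exposure per patient.** Up to 12 − 3 = 9 months for restarting, or 12 − 0.92 = 11.08 months for stopping, would require the divergent state to persist at every visit to month 12. Nothing in the protocol shows that.
- **A threshold that is hard to reach.** Setting 50 µm against the mean falls in thickness in sections 2.3 and 2.4 does not show this. Those are group means that include non-responders, whereas restart concerns only eyes that had resolved.
- **A third rule in section 4.2.** The 12-month period there is loose summary wording beside the up-to-twelve-months wording of section 1.

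**What to change.** Keep one restart trigger, in the rules paragraph of section 4.5. There are two ways to do it:

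- delete the 50 µm criterion from the opening part, so that any recurrence of sub-foveal fluid restarts treatment; or
- move the criterion into the rules paragraph, so that restart needs recurrent sub-foveal fluid and a CSRT rise of at least 50 µm measured from the visit at which drug was stopped.

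The choice is clinical; either leaves a single rule. Then align the stop wording in the opening part with the rules paragraph, so that treatment continues until fluid under the fovea of the study eye has fully resolved. Leave the reference to the study eye as it is: narrowing it to the primary eye would be a new dosing rule for bilateral cases. Section 4.2 needs no change for this point.

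The cost is a protocol amendment and a note to sites. Section 9.1 requires ethics approval before implementation, and the amendment log shows regulator approvals for earlier changes, so this is more than an editorial correction. No visit or measurement is added, because Table 1 already schedules OCT at week 4 and months 3, 6, 9 and 12. If restarts have already occurred, the trigger used for each should be listed.

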## 4.6 Primary and secondary outcomes

### 4.6.1 Primary outcome

The primary outcome is the BCVA at the 12 month visit, adjusted for baseline BCVA, measured using validated ETDRS vision charts with measurements made in accordance with a standardised protocol for trials in medical retina. Refracted visual acuity will be done at baseline, 4 weeks, 3, 6 9 and 12 months.

### 4.6.2 Secondary outcomes

Secondary outcome measures are:

1. Low luminance BCVA. This is measured immediately after measuring BCVA by adding a 2 log neutral density filter and recording the number of letters read.
2. CSRT as measured by OCT recorded at 12 months, including CSRT measured at interim visits and adjusted for baseline CSRT.
3. Change in sub-retinal fluid thickness as measured by OCT
4. Systemic and ocular adverse events at any time during the 12 month follow-up period
5. Proportion of patients with macular atrophy of the RPE defined as hypoautofluorescence at 12 months
6. Area change in macular RPE hypoautofluorescence at 12 months.
7. Choroidal thickness as measured by enhanced depth imaging OCT at 12 months, adjusted for baseline choroidal thickness. Measurements to be made sub-foveally.
8. Proportion of patients with reduced choroidal permeability on ICG at 12 months
9. Time to resolution of SRF.
10. Classification of all study eyes as complete, partial or no resolution of SRF at each time point of the study. Partial resolution of SRF is defined as a decrease of >25 % of CMT from baseline due to resolution of SRF. A non-responder is defined as having an increase in SRF or decrease in SRF  $\leq 25\%$  from baseline. Recurrence will be defined as the appearance of new SRF in a study eye after complete resolution of SRF at any point.
11. Patient-reported visual function using Visual Function Questionnaire VFQ 25 will be assessed at baseline and 12 months.
12. Classification of all study eyes by each FFA phenotype, such as smoke stack, ink-blot and chronic epitheliopathy
13. Classification of all study eyes as early, late, or non responder. An early responder is defined as complete or partial resolution of sub-foveal SRF by 3 months. A late responder is defined as complete or partial resolution of sub-foveal SRF after 6 months.
14. Incidence of CSCR in the fellow eye as measured by OCT, FFA, ICGA or AF.

A validated ophthalmic reading centre will assess images obtained from OCT, ICGA and FFA at baseline and 12 months.

## 4.7 Sample size calculation

A sample size of 45 patients in each of the 2 groups would be sufficient to detect a difference of 5 letters in BCVA between the eplerenone and placebo groups with 90% power and 5% significance (2-tailed), assuming that the standard deviation is 9 letters [14], the correlation between baseline and any follow up assessment is 0.5 [15], and that, on average, there will be a minimum of 2 follow up assessments per patient [16] with a correlation between BCVA on follow-up visits of 0.8. The total sample size has been increased to 104 to allow for up to 15% dropout over the 12 month period, which should be a conservative estimate in this patient

group. This sample size justification does not take into account the extra power that will be obtained from including data for two eyes, coded as CSCR or not.

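### The 90% power in section 4.7 is for a treatment effect shared by at least two follow-up visits; for BCVA at the 12-month visit, the declared primary outcome, it is about 85–89%

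*Protocol*

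**What the plan says.** Section 4.7 states: "A sample size of 45 patients in each of the 2 groups would be sufficient to detect a difference of 5 letters in BCVA", with 90% power at the two-sided 5% level. The inputs are "assuming that the standard deviation is 9 letters", "the correlation between baseline and any follow up assessment is 0.5", and that "on average, there will be a minimum of 2 follow up assessments per patient [16] with a correlation between BCVA" values at different follow-up visits of 0.8. The cited source for the repeated-measures element is, by its title in the reference list, about analysis with mean summary statistics. The total is raised to 104 for up to 15% dropout.

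Section 4.6.1 defines the outcome differently: "The primary outcome is the BCVA at the 12 month visit, adjusted for baseline BCVA". Section 4.2 likewise tests superiority at 12 months. BCVA is scheduled at five post-baseline visits: week 4 and months 3, 6, 9 and 12.

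Section 6.1 analyses BCVA with a mixed model over all visits, adjusted for baseline. A treatment-by-time term enters only if it is significant at 5%, and the 12-month effect is then reported. Otherwise, by implication, the model carries one treatment effect common to all visits.

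**The concern.** Averaging correlated follow-up measurements reduces variance, and section 4.7 takes credit for that reduction. The credit is legitimate for an effect averaged over visits, or assumed equal at each of them. It does not apply to an effect estimated at month 12 alone, which is what 4.6.1 names and what 6.1 reports when the interaction is significant.

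At stake is the meaning of the headline power. Section 2.2.1 presents the trial as adequately powered for a clinically important visual benefit, and section 7.3.2 asks the DMSC to compare accruing data with the sample size assumptions. Both uses need the power to belong to the declared outcome. A null 12-month result would otherwise be judged against a type II error of 10% when the figure is nearer 11–15%.

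**Working it through.** **Inputs (all from section 4.7).** Difference 5 letters; SD 9, so variance 81; two-sided 5% (z = 1.960); 90% power (z = 1.2816); baseline-to-follow-up correlation 0.5; correlation between follow-up visits 0.8; 45 evaluable per group; 104 randomised (52 per group); 15% dropout.

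**Formulas.** For the baseline-adjusted mean of r follow-up visits, the variance factor is f = (1 + (r − 1) × 0.8)/r − 0.5².
- n per group = 2 × (1.960 + 1.2816)² × 81 × f / 25 = 68.09 × f
- SE = 9 × √(2f/m) with m per group
- power = Φ(5/SE − 1.960)
- difference detectable with 90% power = 3.2416 × SE

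**Reproducing the stated figure (r = 2).** f = 1.8/2 − 0.25 = 0.65, so n = 44.26, rounded up to 45. At 45 per group SE = 1.530 and power = 90.5% (89.8% with the noncentral t). Other constructions do not give 45: unadjusted single visit 69, unadjusted mean of two visits 62, change score 69 (one visit) or 62 (two visits), one-sided adjusted single visit 42.

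**Effect specific to month 12 (r = 1).** f = 1 − 0.25 = 0.75, so n = 51.07, rounded up to 52 evaluable per group. At 45 per group SE = 1.643 and power = 86.1% (85.3% with the noncentral t); the detectable difference is 5.3 letters.

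**Same effect with 104 randomised and 15% dropout.** This leaves 52 × 0.85 = 44.2 completers and 7.8 dropouts per group. Given baseline, the residual variance at each visit is 81 × 0.75 = 60.75 and the covariance between visits is 81 × (0.8 − 0.25) = 44.55.

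| Data from dropouts | SE | Power at 5 letters | Difference for 90% power |
|---|---|---|---|
| None | 1.658 | 85.4% | 5.4 letters |
| Last visit attended spread evenly from none to month 9 | 1.593 | 88.1% | 5.2 letters |
| All visits except month 12 | 1.572 | 88.9% | 5.1 letters |

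The last row can be checked by hand. The four earlier visits explain R² = 4 × 0.55² / [(0.75 + 3 × 0.55) × 0.75] = 0.672 of the residual variance at month 12. Then SE² = 2 × 60.75 × (0.328/44.2 + 0.672/52) = 2.47, so SE = 1.572. With no dropout, 52 per group give SE = 1.529 and 90.5%.

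**Default model of 6.1: one effect common to all five visits.** f = (1 + 4 × 0.8)/5 − 0.25 = 0.59. At 45 per group SE = 1.457 and power = 92.9%, if the effect is 5 letters at every visit from week 4 on.

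**What the common effect measures if the effect builds up.** Suppose, as an illustration, that it rises in a straight line to 5 letters at month 12, taking week 4 as month 1. The five-visit average is then 5 × (1 + 3 + 6 + 9 + 12)/(12 × 5) = 2.6 letters, which is not the 12-month effect.

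**The case against.** The strongest reply is that section 6.1 analyses all visits. Its default model has one treatment effect, and 4.7 may be read as sizing the trial for that estimator, conservatively, since it credits two visits where five are scheduled. This largely stands for a constant effect: simulating the 6.1 rule with the 4.7 covariance and a constant 5-letter effect gives about 92% power. It is therefore tempting to conclude that the 90% is simply wrong, that earlier visits add nothing, or that 90% needs all 52 per group complete. The protocol does not support those readings without a condition. They hold only for a 12-month-specific effect, and the statement about earlier visits needs complete data as well.

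The reply does not remove the point, because 4.7 never states the constant-effect assumption and the protocol gives grounds to doubt it. In the pilot (section 2.3) mean BCVA was still moving between 1 and 3 months, from 0.34 to 0.27 LogMAR. Section 4.6.2 distinguishes early from late responders, and under section 4.5 treatment stops on resolution and may restart. If the effect builds up to 5 letters by month 6 or month 12, the same simulated rule gives roughly 83–87%.

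The second reply is that the gap is small. This stands. Section 5.12 expects about 5% withdrawal and 5% loss to follow-up; with 10% loss and no partial data, single-visit power is 87.4%, and with the 4% annual loss quoted in section 4.3.3 it is 89.3%. An SD of 8.5 instead of 9 would give 89.7% at 45 per group, and a baseline correlation of 0.6 would give 90.9%. Section 4.7 also leaves out any gain from second eyes, but gives no figure that could offset the gap.

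**Conclusion.** The point holds in a limited form. The 90% in 4.7 is the power for an effect averaged over, or constant across, at least two follow-up visits. For the 12-month effect named in 4.6.1 and 4.2, power at 5 letters is about 86% with 45 evaluable per group, and about 85–89% with 104 randomised and 15% dropout. The shortfall is thus about 1 to 5 percentage points, or 0.1 to 0.4 letters in the detectable difference. These figures take the SD and correlations in 4.7 as given and, for the dropout range, data missing at random.

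A reader might infer that the trial is seriously underpowered or must recruit more. The documents do not support that: the stated 90% is met under the default model of 6.1 if the effect is constant from week 4. Type I error, randomisation and data collection are unaffected, and 6.1 provides for a 95% confidence interval from which a null result can be read. The defect is a power statement tied to a different quantity from the named outcome, with its linking assumption unstated. Its importance is moderate.

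**What to change.** - In 4.7, state that 90% power with 45 per group applies to a treatment effect common to the follow-up visits.
- Beside it, give the power for the 12-month contrast: about 85–89% for 5 letters with 104 randomised and 15% dropout, or 90% power for about 5.1–5.4 letters.
- Align 4.6.1, 4.7 and 6.1 on which effect is primary: the effect at 12 months, or the effect common to all visits. The average-over-visits effect should not be labelled secondary, because 4.6.2 lists no such outcome and under 6.1 it is the default estimate for BCVA.

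The cost is a rewording of these sections. No extra patients, visits or measurements are needed. The only drawback is a slightly less favourable stated power.
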